2.2 Study variable(s)

2.2.1 Primary variable(s)

The primary outcome of this observational study is malignancy (malignant tumors and malignant or unspecified tumors). Additionally, the following safety events will be presented using incidence and event rates, and time-to-event statistics:

- Serious infections
- Opportunistic infections
- Serious cardiovascular events (also called major adverse cardiac events, or MACE)
- Congestive heart failure
- Demyelinating-like disorders
- Aplastic anemia, pancytopenia, thrombocytopenia, neutropenia and leucopenia
- Serious bleeding events
- Lupus and lupus-like illness
- Serious skin reactions

Although not officially AEs of interest, the following events will also be summarized as described in the AEs of Interest – Cimzia Program 2018-06-18 guidance document.

- Hepatic Events
- Hypersensitivity reactions and anaphylactic reactions

Separate from the AEs of interest document, malignant lymphomas, non-melanoma skin cancer, and autoimmune disorders will also be summarized.

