2.3.1 Patient Inclusion/Exclusion Criteria

Patients who meet all of the following criteria will be eligible for inclusion into the SECURE Registry:

- Patient (or his/her legally acceptable representative) is able to provide written informed consent to permit collection of data.
- Patient must be 18 years of age or older.
- Patient must have medically documented CD.
- The decision to prescribe Cimzia or other medications has been made by the physician independently of the decision to include the patient in the study.
- Patients participating in randomized, blinded clinical trials for CD or other conditions are not eligible for inclusion into the SECURE registry. Involvement in other registries, where patients follow routine clinical practice, is permitted, however.
- The rules for handling erroneous patient entries are laid out in a separate Analysis Data Reviewers Guide.

Cimzia-treated patients

For a patient to qualify as being treated with Cimzia, they must meet one of the following criteria:

- Patient is receiving treatment with Cimzia for the first time. Patient must receive Cimzia treatment within 2 months of enrollment into the registry.
- Patient is currently receiving treatment with Cimzia for ≤ 12 months. Patients must also receive a Cimzia dose within 2 months following enrollment into the registry.

Comparator patients

Patients enrolled in the comparator group are eligible to participate in the registry if one of the following criteria is fulfilled:

- Patient is switching CD treatments or beginning CD treatment for the first time. Previous Cimzia treatment is prohibited in the comparator group. Patient must receive new CD treatment within 2 months of enrollment into the registry.

- Patient is currently receiving other biologic treatment (excluding Cimzia) for ≤ 12 months. Patient must receive other biologic treatment within 2 months following enrollment into the registry.
- Patient is currently receiving immunosuppressant therapy for ≤ 12 months. Patient must receive immunosuppressant therapy within 2 months following enrollment into the registry.
- Patient is currently receiving systemic steroid therapy for ≤ 12 months. Patient must receive systemic steroid therapy within 2 months following enrollment into the registry.

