3.2.1 Exposure

Cancer progresses in several stages before reaching a detectable, malignant state. While this latency period may differ by cancer type, it is generally believed to occur over a long period of time (3). Thus, a treatment-related event may not be seen until years after the initial exposure. In contrast, acute events typically have very short latency periods; therefore, it is unlikely that a treatment-related event will occur after exposure to the product has ended. For the primary endpoint analysis, 2 different methods of person time calculations will be used, one for malignancy events (Section 3.2.1.1) and one for acute events (Section 3.2.1.2).

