3.2.1.1 Person-time at risk calculations for malignancy

Due to the long latency of malignancy, gaps in exposure between treatments will be attributed to the most recent, previous treatment. Gaps in exposure before first known treatment will not be factored into person-time calculations for these events. Any patient exposed to Cimzia during the study will only contribute person-time to the Cimzia cohort from that point onward (Figure 1). As an example, if a malignancy should occur any time after Cimzia exposure (including when Cimzia was known to be used prior to enrollment), it will be attributed to Cimzia. If a malignancy occurred in a patient prior to Cimzia exposure or in a patient with no Cimzia exposure, then it would be attributed to comparator. Thus, a patient may have exposure to multiple comparator drugs, but any malignancies diagnosed after treatment with Cimzia would be systematically attributed to Cimzia, even after ending or switching from Cimzia.

Figure 1: Example person-time at risk for malignancy events

Exposure person-time at risk will be calculated for each CD treatment using the following equation:

$$\text{Last Date} - \text{First Date} + 1$$

where all person-time is contributed to Cimzia after first Cimzia dose is administered.

First date is defined as the latest enrollment date or first CD treatment date after enrollment (whichever is later) or first Cimzia dose date if switching from a comparator treatment after enrollment. Last date is defined as the earliest of the following:

- Date of safety event of interest (for incidence rate calculations only)

- Date of discontinuation, withdrawal, or data cutoff

See Section 11.1, appendix 1 for more examples of treatment allocation scenarios for malignancies.

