Per patient and Adverse Event of Interest, exposure time up to the first occurrence of the AE is considered. The attribution of the AE to Cimzia or Comparator follows the exposure rules as described in Section 3.2.1.1, i.e., if the patient was exposed to Cimzia, prior to the AE, the event will be systematically attributed to Cimzia, irrespective of actual treatment. If the patient was not exposed to Cimzia prior to the AE, it will be attributed to Comparator. Exposure to Comparator prior to a first treatment switch to Cimzia will be attributed to Comparator. As detailed in Section 3.2.1.1, Exposure time is measured from first exposure to Cimzia (or Comparator), irrespective of treatment gaps. If no AE of interest occurred, time will be censored at the end of exposure.

All time-to-event analyses are exploratory and not confirmatory. No formal hypothesis testing will be conducted. P-values are for descriptive purposes only.

The number and percentage of patients with AEs of interest, as well as those censored, will be displayed. Time-to-AEs of interest will be summarized using the Kaplan-Meier method and displayed graphically when appropriate. Median and 25th and 75th percentile event times, with corresponding 2-sided 95% confidence intervals as well as the range of event times will be provided by treatment group. The estimated hazard ratio, 2-sided 95% confidence interval and exploratory p-value will be provided.

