- Serious skin reactions (eg, Stevens-Johnson Syndrome, toxic epidermal necrosis, and erythema multiforme). These will be manually identified by the study physician from Serious TEAE table.

Although not officially AEs of interest, the following events will also be summarized as described in the AEs of Interest – Cimzia Program 2018-01-05 guidance document.

- Hepatic events. These will consist of a subset of all TEAEs, identified using the following 5 SMQs: Cholestasis and jaundice of hepatic origin; Hepatic failure, fibrosis, and cirrhosis and other liver damage-related conditions; Hepatitis, noninfectious; Liver-related investigations, signs and symptoms; and Liver-related coagulation and bleeding disturbances.
- Hypersensitivity reactions and anaphylactic reactions. Hypersensitivity reactions will be summarized as any TEAEs occurring on the same day or the day after injection was received, which code to the following preferred terms: Administration site hypersensitivity, Documented hypersensitivity to administered product, Drug hypersensitivity, Hypersensitivity, Hypersensitivity vasculitis, Infusion site hypersensitivity, Injection site hypersensitivity, Medical device site, hypersensitivity, Type II hypersensitivity or Type IV hypersensitivity reaction. Anaphylactic reactions will be defined using an algorithmic approach as described in the “AEs of Interest – Cimzia Program 2018-01-05” guidance document.
- Specific to study and not from the “AEs of Interest – Cimzia Program 2018-01-05” guidance document, we will also look at Malignant Lymphomas using the Narrow PTs from the “Malignant Lymphomas” SMQ, and into Autoimmune disorders and Lupus/Lupus-Like syndromes.
- Specific to study and not from the “AEs of Interest – Cimzia Program 2018-01-05” guidance document, we will also look at cases of non-melanoma Skin Cancer. These will be manually identified by the study physician from the TEAE table.

Table 8.1: Overview of malignancy events and acute events in this study

Overview of Events	
Event	Event Type (Malignancies are in addition analyzed following acute rules)
Malignant or unspecified tumor	Malignancy
Malignant tumor	Malignancy
Non melanoma skin cancer	Malignancy
Malignant Lymphoma	Malignancy
Serious infection	Acute
Opportunistic infection	Acute
Serious cardiac event	Acute
Congestive heart failure	Acute
Demyelinating-like disorder	Acute
Aplastic Anemia	Acute
Serious bleeding	Acute
Lupus and Lupus-like illness	Acute

Serious skin reaction	Acute

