11 APPENDICES

11.1 Appendix 1 – Treatment Allocation of Malignancies and Acute Adverse Events

Assumptions:

- Treatment periods described in the dosing column have the drug half-life added to the end of each treatment.
- Overlap is when comparator and Cimzia treatment periods overlap. The overlap can occur during the extended treatment for the drug half-life.
- Abbreviations; IC=Informed Consent Date, EoS= End of Study Date
- Gap and Overlap are not possible treatment groups for Malignancy Time at Risk as per SAP section 3.2.1.1 “Person-time at risk calculations for malignancy”. Overlap would be considered Cimzia and Gap would be assigned to the prior treatment.
- The dosing prior to IC only has an impact on malignancy time at risk. If a subject has no Cimzia dosing prior to IC it is considered to have had Comparator dosing prior to IC regardless of what is recorded in the dosing information.

#	Dosing prior to IC	Dosing during study (IC onwards)	Adverse Event	Treatment AE assigned to	Malignancy Time at Risk		Other AE Time at Risk			
					Cimzia	Comparator	Cimzia	Comparator	Gap	Overlap
1a	No Cimzia	Comparator > Cimzia > Comparator	None	N/A	Start of Cimzia to EoS	IC to Start of Cimzia	Start of Cimzia to Start of Second Period of Comparator	(IC to Start of Cimzia) plus (Start of Second Period of Comparator to EoS)	None	None
1b	Cimzia	Comparator > Cimzia > Comparator	None	N/A	IC to EoS	None	Start of Cimzia to Start of Second Period of Comparator	(IC to Start of Cimzia) plus (Start of Second Period of Comparator to EoS)	None	None

#	Dosing prior to IC	Dosing during study (IC onwards)	Adverse Event	Treatment AE assigned to	Malignancy Time at Risk		Other AE Time at Risk			
					Cimzia	Comparator	Cimzia	Comparator	Gap	Overlap
2a	No Cimzia	Comparator > Cimzia > Comparator	Malignancy during second period of Comparator	Cimzia	Start of Cimzia to Malignancy Start Date	IC to Start of Cimzia	Start of Cimzia to Start of Second Period of Comparator	(IC to Start of Cimzia) plus (Start of Second Period of Comparator to EoS)	None	None
2b	Cimzia	Comparator > Cimzia > Comparator	Malignancy during second period of Comparator	Cimzia	IC to Malignancy Start Date	None	Start of Cimzia to Start of Second Period of Comparator	(IC to Start of Cimzia) plus (Start of Second Period of Comparator to EoS)	None	None

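### Malignancies and person-time count towards Cimzia from the first dose with no lag, and no lagged rate or hazard ratio is planned for the primary outcome

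*SAP*

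**What the plan says.** SAP 2.2.1 states: "The primary outcome of this observational study is malignancy". SAP 3.2.1 gives the reason for treating it differently from acute events: latency varies by cancer type, is generally thought to be long, and so "a treatment-related event may not be seen until years after the initial exposure".

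The counting rule follows in SAP 3.2.1.1. An event goes to Cimzia "if a malignancy should occur any time after Cimzia exposure", known use before enrolment included, and "all person-time is contributed to Cimzia after first Cimzia dose is administered". This continues to the end of the study, also once the patient has stopped Cimzia or moved to another drug. SAP 3.6 and Protocol 6.4.1.1 use the same rule. For the time-to-event analysis under malignancy rules, SAP 8.1.3 says: "Exposure time is measured from first exposure to Cimzia (or Comparator), irrespective of treatment gaps". Appendix 1 applies it. In case 2a the Cimzia time at risk is "Start of Cimzia to Malignancy Start Date". For patients with Cimzia use before consent (for example cases 1b, 2b and 8a), it starts at informed consent.

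Prior users are admitted under SAP 2.3.1: "Patient is currently receiving treatment with Cimzia for ≤ 12 months". No minimum time since first dose is set anywhere.

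**The concern.** The latency argument is applied at one end only. It justifies counting cancers against Cimzia long after the last dose, but is not used to set aside the period just after the first dose, when a diagnosed cancer may well have been developing already.

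Two opposite distortions follow. Cancers that began during comparator treatment, or before any treatment, but are diagnosed soon after a switch raise the Cimzia rate. If a true effect appears only late, early Cimzia person-time with no effect in it pulls the ratio towards 1. A ratio near 1 and a raised ratio are then both hard to interpret, and the plan has no estimate that would separate the explanations.

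**Working it through.** **1. Is there a lag anywhere in the planned malignancy analyses?**

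- Main rates and hazard ratio (SAP 3.2.1.1, 8.1.3, 8.1.4, Appendix 1): lag of zero.
- Acute rules (Table 8.1: "Malignancies are in addition analyzed following acute rules"): these keep early on-drug events and leave out of the Cimzia count those beyond the 70-day window for biologics. That is the reverse of a lag.
- Cumulative Cimzia exposure strata (SAP 8.2.1): optional, no cut-points, and based on amount of exposure rather than time since first dose.
- Tabulations (SAP 8.1.1): number, order and type of treatments, not time since start.
- Incident/prevalent stratification (SAP 4.5, 8.1.5): acute events only.
- Propensity scores and regression (SAP 8.1.2, 8.1.5): baseline covariates only.
- Kaplan-Meier summaries (SAP 8.1.3): event-time percentiles and range by group, which show timing in part. The hazard ratio still averages over all time.

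**2. What the rule does at a switch.** In Appendix 1, case 14a, a cancer found in the gap before Cimzia starts is a comparator event. In case 8b, a cancer found once Cimzia has started is a Cimzia event, with no minimum interval. Two similar tumours diagnosed days apart, either side of the first dose, fall in different groups. The documents give no figure from which the size of this inflation could be worked out.

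**3. Size of the possible dilution.** The plan has no figure for a lag, so there is none to reproduce. The nearest is the expected 25,000 person-years (Protocol 6.3, SAP 2.4), which is not used below.

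Inputs: 8 years of follow-up and 8% annual drop-out (Protocol 6.3); detectable ratios of 1.56 for solid malignancies and 3.3 for lymphoma (same section), used here only as example effects. Assumptions: the patient starts Cimzia at enrolment, the background cancer rate is constant, and there is no effect before the lag and the full ratio after it. The lag lengths are also assumptions.

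Person-years per patient to time t: P(t) = (1 − 0.92^t) / (−ln 0.92), with −ln 0.92 = 0.0834.

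- P(0.5) = 0.490; P(1) = 0.959; P(2) = 1.842; P(8) = 5.838.
- Early share s = P(lag)/P(8): 0.490/5.838 = 8.4%; 0.959/5.838 = 16.4%; 1.842/5.838 = 31.6%.
- Averaged ratio = s + (1 − s) × RR.

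| Lag | Early share | Later ratio 1.56 averages to | Later ratio 3.3 averages to |
|---|---|---|---|
| 6 months | 8.4% | 1.51 | 3.11 |
| 12 months | 16.4% | 1.47 | 2.92 |
| 24 months | 31.6% | 1.38 | 2.57 |

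**4. How far the share moves for other patients (12-month lag).**

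- Six months of Cimzia before enrolment: only the first 6 months of counted time fall inside the lag, 8.4%. Twelve months before: 0%.
- Switch to Cimzia 3 years after enrolment, 5 years left: P(5) = (1 − 0.659)/0.0834 = 4.09, and 0.959/4.09 = 23%.
- New starter enrolled at the end of March 2017, followed to the study end on 28 August 2020 (SAP 2.3), about 3.4 years: P(3.4) = (1 − 0.753)/0.0834 = 2.96, and 0.959/2.96 = 32%.

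**The case against.** The strongest defence is that the ever-exposed rule is a deliberate choice that misses no late Cimzia cancer, in a registry whose analyses are descriptive. Event timing is not invisible either. SAP 8.1.3 requires event-time percentiles and the range by group, measured from first exposure, and SAP 8.1.1 tabulates treatments up to onset. If the effect were constant from the first dose, a lag would only discard information.

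Much of this stands. It argues for keeping the main rule and against any claim that the plan shows nothing about timing. It does not supply a lagged estimate.

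A reader might also infer stronger points that the documents do not support:

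- *That the SAP says effects take years, so early Cimzia cancers cannot be due to Cimzia.* SAP 3.2.1 says only that an event may appear late and that latency may differ by cancer type.
- *That the primary ratio is biased in a known direction.* Inflation at switches and dilution of a late effect work against each other.
- *That the stated 80% power falls by a calculable amount.* SAP 2.1.1 and 8.1 plan no formal test. The 80% rests on 25,000 person-years, while 3,045 × 5.838 is about 17,800. No control rate is given, and 1.56 refers to solid malignancies only, not to the whole primary outcome.
- *That 16% applies to the whole cohort.* It is the case of a new starter at enrolment with full follow-up.

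**Conclusion.** The point holds in limited form. The SAP's latency reasoning supports carrying attribution forward after Cimzia stops, but the same reasoning is not applied at the start, and no planned malignancy analysis gives a lagged rate or hazard ratio. The direction of bias is open.

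On the stated assumptions, 12 or 24 months hold about 16% or 32% of a new starter's person-time, and a later ratio of 1.56 would be reported as about 1.47 or 1.38. Prior use makes the share smaller; later switching and the August 2020 study end make it larger. No power claim is made. The main analysis can stand. What is missing is a sensitivity analysis on the primary outcome that uses treatment and event dates the plan already works with.

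**What to change.** Keep the ever-exposed rule as the main analysis. Add to SAP 8.1.1 and 8.1.3 a sensitivity analysis for the malignancy endpoints of Table 8.1, giving rates (as in 8.1.4) and hazard ratios with a 12-month lag, repeated at 6 and 24 months. The sponsor should justify these lengths and fix them before seeing lagged results. The text should state:

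- **Cimzia:** events and person-time count once the lag since the first Cimzia dose has passed. Recorded use before enrolment counts towards the lag.
- **Patients who switch to Cimzia:** time and events within the lag after the switch are excluded from both groups, not returned to comparator.
- **Comparator:** the same lag runs from the first recorded dose of any drug in the three comparator classes of SAP 3.2. Recorded dates are used, not the Appendix 1 convention that treats every patient without earlier Cimzia as having had comparator dosing. Otherwise the lag would remove time from new Cimzia starters but little from the comparator.

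Cost: three lags for four endpoints, so 12 sets of estimates from one program. These runs lose about 16% of person-years at 12 months and 32% at 24 months for new starters with full follow-up (less with prior use, more with shorter follow-up), plus the events in that time. Precision is lower if the effect is constant from the first dose, which is why this belongs beside the main analysis and not in its place.

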3.2.1.2 Person-time at risk calculations for acute events

Exposure person-time at risk will be calculated for each CD treatment using the following equation:

$$\text{Last Date} - \text{First Date} + 1$$

First date is defined as the latest enrollment date or first CD treatment date after enrollment (whichever is later) or the first dose of new treatment if switching treatments. Last date is defined as the earliest of the following:

- Date of safety event of interest (for incidence rate calculations only)
- Last dose date + treatment class-specific half-life exposure for product
- Date of discontinuation, withdrawal, or data cutoff

Any gaps in exposure, as illustrated in the figure below, will be included in the gap treatment group person-time at risk calculations for acute events. Any overlap in treatment groups will be included in the overlap group person-time at risk calculations for acute events.

Figure 2: Example person-time at risk for acute events

[figure not shown]

Figure 2 presents an example of a patient's exposure history. For this example, exposure person-time at risk would be calculated as follows:

Exposure person-time = (Last treatment date + Treatment class-specific half-life) – First treatment date + 1) + (earliest of End treatment date + treatment class-specific half-life exposure, last date in study, data cutoff date) – Resume treatment date + 1).

See Section 11.1, appendix 1 for more examples of treatment allocation scenarios for acute events.

3.2.1.3 Determination of Event Rate Numerator

The number of events will be determined for Cimzia and for all other CD treatments considered comparator treatments based on the date of the last dose received before event onset and treatment class-specific half-life exposure of the medication. The exposure half-lives used for rate calculations for each treatment class are as follows:

- Corticosteroids: 7 days
- Immunosuppressants: 28 days
- Biologic agents (including Cimzia): 70 days

3.2.2 Physician reported Harvey-Bradshaw Index

The physician reported Harvey-Bradshaw Index (HBI) is composed of 5 parameters:

1. General well-being (0=Very well, 1=Slightly below Par, 2=Poor, 3=Very poor, 4=Terrible)
2. Abdominal pain (0=None, 1=Mild, 2=Moderate, 3=Severe)
3. Number of liquid stools per day
4. Abdominal mass (0=None, 1=Dubious, 2=Definite, 3=Definite and tender)
5. Complications (1 per item: Arthralgia, Uveitis, Erythema nodosum, Aphthous ulcers, Pyoderma gangrenosum, Anal fissure, New fistula, and Abscess)

Note for #3 that if a patient is using a colostomy bag, the number of times per day the bag is emptied is counted instead.

The use of eCRFs in this registry will allow the total score to be computed and, therefore, not require the investigators to record the total HBI score. If any of the first 4 parameters are missing, then the total HBI score will be set to missing. Otherwise, the total will be the sum of available data.

In cases where HBI is collected multiple times in the same visit a worst case approach will be taken.

HBI response, determined based on physician reported HBI total scores, is defined as a drop of at least 3 points from baseline HBI total score.

HBI remission, determined based on physician reported HBI total scores, is defined as an absolute score of 4 points or less.

